5.3.1.2. Viral kinetics

The viral culture (TCID₅₀) measurements are analyzed using two methods (depending on influenza subtype); i.e. NP ELISA and Hemagglutination Inhibition Assay. For analysis purposes the results from the NP ELISA method will be used when available, otherwise the results from the Hemagglutination Inhibition Assay will be used. This will be determined per analysis visit. As a consequence, the series of results of a subject can be a combination of both methods (for example at baseline the NP ELISA result is used and at Day 3 the Hemagglutination Inhibition Assay result is used).

Endpoints listed below will be based on results from nasal mid-turbinate (MT) swabs taken from central testing, excluding data from leftover samples from local virology tests.

Measurement	Formula
Log ₁₀ viral load actual values	Log ₁₀ of the actual values as measured with qRT PCR
Viral load negativity (Log ₁₀ vp/mL)	
Viral load will be categorized as Negative or Positive:
 
 • Negative (“TARGET NOT DETECTED”) • Positive (‘TARGET DETECTED’ or an actual value).

Viral load categorization (Log ₁₀ vp/mL)	Viral load will be categorized as Target not detected, Target detected, and Quantifiable: 
 • Target not detected • Target detected • Quantifiable
Log ₁₀ viral load change from baseline	Log ₁₀ viral load post-baseline value – log ₁₀ viral load baseline value
Log ₁₀ viral titer actual values	Log ₁₀ of the actual values as measured with viral culture
Viral titer negativity (Log ₁₀ TCID ₅₀ /mL)	Viral titer will be categorized as Negative or Positive: 
 • Negative (lower than LOQ) • Positive (quantifiable results)
Log ₁₀ viral titer change from baseline	Log ₁₀ viral titer post-baseline value – log ₁₀ viral titer baseline value
Viral load AUC _{0-10d} trapezoidal method	
■ Viral load AUC calculated from baseline to Day 10:
 
AUC is calculated by the trapezoidal summation rule, based on planned days of sampling, including the timepoints with (imputed) values available:
 $\text{Sum over } i \text{ of } (t_{i+1}-t_i) * (\text{Viral load}_{i+1} + \text{Viral load}_i) / 2$ 
The following rules will be applied in the order described below to deal with missing values before calculating the Viral load AUC:
 
 • If the baseline value is missing, then the mean baseline value over all subjects in the ITT-i set will be used. • If a single or sequential intermediate value (not the baseline value) is missing, then the missing value will be replaced by linear interpolation of the two adjacent values. Note: this is done automatically when applying the trapezoidal summation rule. If Day 10 value is missing, but there is an assessment after Day 10, then this value will be used to interpolate the value of Day 10. • If the Day 10 value is missing, and there are no values available after Day 10, then it will be imputed with the last observed post-baseline value (LOCF). 
Note: In case no post baseline value is available the AUC will be missing.


Viral titer AUC_{0-10d} trapezoidal method
	
Viral titer AUC calculated from baseline to Day 10:
 
AUC is calculated by the trapezoidal summation rule, based on planned days of, including the timepoints with (imputed) values available:
 $\text{Sum over } i \text{ of } (t_{i+1}-t_i) * (\text{Viral titer}_{i+1} + \text{Viral titer}_i) / 2$ 
The following rules will be applied in the order described below to deal with missing values before calculating the Viral titer AUC:
 
 • If the baseline value is missing, then the mean baseline value over all subjects in the ITT-i set will be used. • If a single or sequential intermediate value (not the baseline value) is missing, then the missing value will be replaced by linear interpolation of the two adjacent values. Note: this is done automatically when applying the trapezoidal summation rule. If Day 10 value is missing, but there is an assessment after Day 10, then this value will be used to interpolate the value of Day 10. • If the Day 10 value is missing, and there are no values available after Day 10, then it will be imputed with the last observed post-baseline value (LOCF). 
Note: In case no post baseline value is available the AUC will be missing.

Time to viral negativity by qRT-PCR (days) [Time-to event]
	
The time to viral negativity is defined as the time (in days) from first study drug intake until a subject is considered influenza A viral negative. This is the first timepoint of two consecutive timepoints with a negative nasal MT swab, i.e. the first and next assessment equal to 'negative' (ignoring missing values). In case the first 'negative' is the last available assessment the subject is considered to have reached viral negativity at this last assessment.
 
If this doesn't occur, a subject will be censored at the time of the last observed non-negative swab + 1 day. Note that for deriving the time to viral negativity by qRT-PCR every subject is considered positive at baseline. For subjects without postbaseline records, they are censored at Day 1.

Time to viral negativity by viral culture (days) [Time-to event]
	
The algorithm for Time to viral negativity by viral titer is similar as 'Time to viral negativity by viral load' but viral titer assessments are used instead.

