 - k. Central virology testing: Nasal MT swabs should be obtained from the left and the right nostrils (from both nostrils if feasible, but from only one nostril otherwise) and pooled into the same collection tube. In case the subject is intubated, endotracheal samples should be taken as well, at the same time as the nasal MT swab. The samples will be collected at screening/baseline and on Days 2, 3, 4, 5, 8, 10, and 14. The screening/baseline sample needs to be collected predose, as close as possible to the first dose. Sampling should be done at approximately the same time (± 4 hours) on each sampling day. Leftovers from nasal MT swabs and endotracheal samples collected for virology testing may be used for protein biomarker analysis, if not restricted by local regulations.
 - l. At the time points where both nasal MT swabs/endotracheal aspirate and pharmacokinetic (PK) samples are obtained, these samples should be obtained as close together in time as possible.
 - m. Vital signs include body temperature, pulse rate, respiratory rate, and blood pressure. For peripheral capillary oxygen saturation, it should be recorded whether the measurement was with or without supplemental oxygen. The SpO₂ should be measured either in a sitting or supine position after 5 minutes of rest in a quiet environment.
 - n. National Early Warning Score (NEWS2) should be calculated before randomization as NEWS2 at baseline is an inclusion criterion (≥ 4) as well as a stratification factor (4-5 or >5).
 - o. Vital signs/peripheral capillary oxygen saturation (pulse oximetry)/ACVPU are to be evaluated 3 times daily: in the morning (prior to study drug intake if applicable), approximately half-way in the middle of the day, and in the evening (prior to study drug intake if applicable).
 - p. Questionnaire (Return to daily activities) to be completed at screening/baseline (as close as possible to the first dose) and then once daily onto the ePRO device.
 - q. Questionnaire (PGIS) to be completed at screening/baseline (as close as possible to the first dose) and then once daily onto the ePRO device.
 - r. Questionnaire (PGIC) to be completed on Days 6, 14, and 28 onto the ePRO device.
 - s. Questionnaire (EQ-5D) to be completed at screening/baseline (as close as possible to the first dose) and on Days 6, 14, and 28 onto the ePRO device.
 - t. Follicle-stimulating hormone (FSH) will be tested at screening for female subjects who are amenorrheic for 12 months or less.

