2. TIME AND EVENTS SCHEDULE – AFTER DISCHARGE FROM HOSPITAL

Note: This Time and Events Schedule should start with the study day number following the day of discharge from the hospital (for example: subjects discharged on Study Day 3 would start with Day 4 procedures on this schedule). After subjects are discharged, the remainder of the study visits should be carried out as outpatient visits (preferably on-site or, if not feasible, at the subject's home) or by telephone follow-up as indicated in the table below. Every effort should be made to perform all of the assessments as outlined below (either on-site or at the subject's home), if practically feasible. In case of readmission to the hospital, subjects will continue to follow this Time and Events Schedule until the end of the study.

Phase Day	Treatment ^{a,b} 2/3/4/5	Follow-up ^b						
		6 ^c	7-9	10 +/-1 Day	11-13	14 +/-1 Day	15-27	28 +/-1 Day
	Phone Follow-up ^e						Phone Follow-up ^f	Safety Follow-up Visit / Final Study Visit ^b
Clinic or home visit		X		X		X		X
Administration								
Administration of study drug ^{a,g}	X							
Virology								
Nasal MT swab for central testing ^h		X ⁱ		X		X		
Efficacy/Safety								
Vital signs/pulse oximetry ^j		X						X
Physical exam								X
Symptom-directed physical exam		X		X		X		
12-lead ECG ^k								X
Pregnancy test (female subjects of childbearing potential)	X ^l							X
Influenza Symptom Diary ^{s,t}		2x daily through the Final Study Visit/Safety Follow-up Visit ^d						
Assessment of daily activities resumption ^{m,t}		1x daily through the Final Study Visit/Safety Follow-up Visit ^d						
PGIS ^{n,t}		1x daily through the Final Study Visit/Safety Follow-up Visit ^d						
PGIC ^{o,t}		X ^d				X ^d		X
EQ-5D ^{p,t}		X ^d				X ^d		X
Hematology, chemistry		X ^q				X ^q		X ^q
Urinalysis		X				X		X
Pharmacokinetics		X ⁱ						
Taste and swallowability	X ^r							
Adverse events recording	X	X		X		X	X	X
Prestudy and concomitant medication recording	X	X		X		X	X	X

Abbreviations: ECG: electrocardiogram; EQ-5D: European Quality of Life 5 Dimensions; MT: mid-turbinate; PGIC: Patient Global Impression of Change; PGIS: Patient Global impression of Severity.

- a. If the subject is discharged during study treatment, he/she will receive study drug for at-home use.

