- b. Subjects who prematurely discontinue study drug treatment for any reason (except withdrawal of consent) will be asked to continue with their remaining study visits and assessment schedule. Subjects who withdraw consent during the treatment or follow-up phase will be offered an optional Safety Follow-up Visit. The optional Safety Follow-up Visit will occur the day of consent withdrawal or the day after and will consist of the same assessments as at the Final Study Visit (Day 28), with optional PRO completion.
- c. The Day 6 visit may be performed on Day 7, although efforts should be made to respect the initial Time and Events Schedule.
- d. PRO completion compliance should be assessed daily by the site staff via the ePRO web platform. Reasons for missing assessment should be documented on the web platform by the site after discussion with the subject.
- e. At minimum, a daily phone contact should be established with the subject to document potential adverse events (AEs) and concomitant medications, and to enquire about compliance with study drug intake (the need for a face-to-face visit, at-home or on-site, is at the investigator's discretion).
- f. During this period, at minimum one phone contact should be established with the subject to document potential AEs and concomitant medications (the need for a face-to-face visit, at-home or on-site, is at the investigator's discretion).
- g. For subjects who receive only 1 dose of pimodivir or placebo on Day 1 (evening), dosing should continue until the morning of Day 6 so that all subjects receive 10 doses in total.
- h. Central virology testing: Nasal MT swabs should be obtained from the left and the right nostrils (from both nostrils if feasible, but from only one nostril otherwise) and pooled into the same collection tube. Samples will be collected on Days 6, 10, and 14. Sampling should be done at approximately the same time (± 4 hours) on each sampling day. Leftovers from nasal MT swabs collected for virology testing may be used for protein biomarker analysis, if not restricted by local regulations.

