- a. Subjects who prematurely discontinue study drug treatment for any reason (except withdrawal of consent) will be asked to continue with their remaining study visits and assessment schedule. Subjects who withdraw consent during the treatment or follow-up phase will be offered an optional Safety Follow-up Visit. The optional Safety Follow-up Visit will occur the day of consent withdrawal or the day after and will consist of the same assessments as at the Final Study Visit (Day 33), with optional PRO completion.
- b. On Day 6, subjects will receive 1 dose (evening) or 2 doses (morning and evening) of study drug as part of the extension phase. For subjects who receive only 1 dose of pimodivir or placebo on Day 6 (evening), dosing should continue until the morning of Day 11 so that the subject receives 10 doses in total during the extension phase.
- c. Central virology testing: Nasal MT swabs should be obtained from the left and the right nostrils (from both nostrils if feasible, but from only one nostril otherwise) and pooled into the same collection tube. In case the subject is intubated, endotracheal samples should be taken as well, at the same time as the nasal MT swab. Samples will be collected on Days 6, 7, 8, 9, 10, 14, and 19. Sampling should be done at approximately the same time (± 4 hours) on each sampling day. Leftovers from nasal swabs and endotracheal samples collected for virology testing may be used for protein biomarker analysis, if not restricted by local regulations.
- d. Vital signs include body temperature, pulse rate, respiratory rate, and blood pressure. For peripheral capillary oxygen saturation, it should be recorded whether the measurement was with or without supplemental oxygen.
- e. Vital signs/peripheral capillary oxygen saturation (pulse oximetry)/ACVPU are to be evaluated 3 times daily: in the morning (prior to study drug intake if applicable), approximately half-way in the middle of the day, and in the evening (prior to study drug intake if applicable).
- f. Subjects should rest in a supine position for at least 5 minutes before ECG collection and should refrain from talking or moving arms or legs. If blood sampling or vital signs measurement is scheduled for the same time point as ECG recording, the procedures should be performed in the following order: ECGs, vital signs, blood draw.
- g. Questionnaire (Return to daily activities) to be completed once daily onto the ePRO device.

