5.3. Major Secondary Endpoints

5.3.1. Definition

Formulae to be used for derived variables, including data conversions, are provided in the tables below.

Note that for time-to event variables the actual date or times that the endpoint is met will be used. For the time-to-event variables, in case of death prior to the event, the subject will be censored using a time-to equal to the maximum time across all subjects.

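### Viral negativity is dated at the swab day, but swab days change with discharge and extension: fit the AFT model with interval-censored event times

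*SAP*

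**What the plan says.** **Event and time.** SAP 5.3.1.2 sets the qRT-PCR event as follows: "This is the first timepoint of two consecutive timepoints with a negative nasal MT swab". A first negative that is also the last available assessment counts too. Otherwise "a subject will be censored at the time of the last observed non-negative swab + 1 day". SAP 5.3.1 adds that for time-to-event variables "the actual date or times that the endpoint is met will be used". Culture follows a similar algorithm.

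**Analysis.** SAP 5.3.2.2 refers to the methods for the clinical time-to-event endpoints: stratified Gehan-Wilcoxon (the primary test), stratified log-rank, Kaplan-Meier, AFT and Cox. Baseline viral load or titer is added as a covariate in the last two. No interval-censored analysis is planned.

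**Swab days (Protocol, Time and Events Schedules).**
- In hospital (Schedule 1, footnote k): "The samples will be collected at screening/baseline and on Days 2, 3, 4, 5, 8, 10, and 14".
- After discharge (Schedule 2, footnote h): "Samples will be collected on Days 6, 10, and 14". Days 2 to 5 are telephone contact only, and footnote c allows that "The Day 6 visit may be performed on Day 7". The switch takes effect the day after discharge: "subjects discharged on Study Day 3 would start with Day 4 procedures on this schedule".
- In hospital on extended treatment (Schedule 3, footnote c): "Samples will be collected on Days 6, 7, 8, 9, 10, 14, and 19".

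**Status.** Protocol 2.1.1 names a superiority objective for time to viral negativity. The endpoint is not among the seven in the confirmatory sequence of SAP 5.1.1.

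**The concern.** Discharge and extension happen after randomization, and the plan compares the arms on both. The plan therefore expects that the arms may be observed on different swab schedules, and then reads the swab day as the day of clearance. Part of any recorded difference can reflect when subjects left hospital and not when they cleared virus. Apart from the comparison, dating at the first negative swab is always late when clearance falls between swabs, so the reported medians are too long in both arms. What is at stake is the time ratio and the medians for a secondary virology endpoint with a superiority objective, by both qRT-PCR and culture.

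**Working it through.** **1. Recorded day for the same true clearance day.** This applies the schedules above, assuming that swabs are taken on schedule (including the day of discharge), none is missing and no subject turns positive again.

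| Status | Day 3 | Day 4 | Day 5 | Day 6 | Day 7 | Day 8 |
|---|---|---|---|---|---|---|
| In hospital, no extension | 3 | 4 | 5 | 8 | 8 | 8 |
| Discharged Day 2 | 6 | 6 | 6 | 6 | 10 | 10 |
| Discharged Day 3 | 3 | 6 | 6 | 6 | 10 | 10 |
| Discharged Day 4 | 3 | 4 | 6 | 6 | 10 | 10 |
| Discharged Day 5 | 3 | 4 | 5 | 6 | 10 | 10 |
| Discharged Day 6 or 7 | 3 | 4 | 5 | 10 | 10 | 10 |
| In hospital, extension | 3 | 4 | 5 | 6 | 7 | 8 |

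Compared with staying in hospital without extension, discharge by Day 5 adds up to 3 days for clearance on Days 3 to 5, subtracts 2 for Day 6, and adds 2 for Days 7 and 8. The difference runs in both directions.

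**2. Size of the planned discharge difference.** Inputs from Protocol 11.3: placebo 30/30/25/5/5/5%, common odds ratio about 0.62, 90% power, and two-sided 5% from 11.4. The proportional-odds sample size is N = 12(z₀.₉₇₅ + z₀.₉₀)² / [ln(OR)² (1 − Σp̄³)], where p̄ is the mean of the two arms' category shares. With 12 × 3.2415² = 126.09, ln(0.62)² = 0.2285 and 1 − Σp̄³ = 0.9175, N = 601.4. Power at 600 is 89.9%, so the plan's figure is reproduced. The implied pimodivir share not hospitalized on Day 6 is 0.30 / (0.30 + 0.70 × 0.62) = 40.9%, against 30%. This is a proxy for being at home, since that category also includes inpatients judged ready for discharge.

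**3. Simulation, Weibull clearance.** Assumptions not in the documents: shape 1.5; median 1.5 to 6 days; early discharges spread over Days 2 to 5 as 10/20/30/40% or equally; 15% per day discharged after Day 5; correlation between clearance and discharge 0 to 0.8. There were 400,000 subjects per arm for bias, and 1,000 trials of 300 per arm for the Gehan test (correlation 0 or 0.5).
- True ratio 1.00, 30% vs 40.9%: planned AFT 1.00 to 1.02; interval-censored AFT 0.998 to 1.007. The Gehan test is significant for slower clearance in 2.4% to 3.8% of trials (nominal 2.5%).
- True ratio 1.00, equal discharge: planned AFT 0.999 to 1.002. Later discharge on pimodivir (22% vs 30%): 0.996 to 1.001.
- True ratio 0.80: planned AFT 0.820 to 0.833 with unequal discharge and 0.815 to 0.828 with equal discharge; interval-censored 0.797 to 0.802. Most of this shrinkage comes from late dating in both arms, not from the discharge difference. Gehan power is 90% to 92% with unequal discharge and 91% to 95% with equal discharge.

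**4. Simulation, log-normal clearance** (sigma 0.6, median 1.5 to 3.5 days, 30% vs 40.9%; all but the last pair assumed).
- True ratio 1.00: planned AFT about 1.00 to 1.02; interval-censored 0.99 to 1.01.
- True ratio 0.85: planned about 0.86 to 0.89; interval-censored 0.85. Since ln(0.86)/ln(0.85) = 0.93 and ln(0.89)/ln(0.85) = 0.72, 7% to 28% of the log effect is lost.
- The fitted placebo median is about 0.6 to 1.1 days too long under the planned rule. For example, true medians of 2.5 and 3.5 days are estimated as 3.3 and 4.5. The interval-censored fit recovers the true medians.

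**5. Limits of the remedy (Weibull model).** With 30% vs 60% discharged early and all early discharges on Day 2, the planned AFT gives 1.01 to 1.22 under no true effect, and the interval-censored AFT 0.99 to 1.07. If the link between discharge and clearance differs by arm (30% vs 40.9%), the ranges are 0.935 to 1.101 planned and 0.965 to 1.018 interval-censored.

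**The case against.** **The direction is not given.** A reader might infer that the plan will make pimodivir look slower to clear virus. That needs earlier discharge on pimodivir. The trial hypothesizes it, but the Phase 2 hospital study in Protocol 1.1 estimated a 13% longer time to discharge. The Day 6 swab also favours subjects already at home. At the planning assumptions no estimate reverses a true benefit. The chance of a falsely significant slower result runs from about 2.4% to 8% across the assumptions tried. The upper end occurs with log-normal clearance (median 3 to 4 days) and early discharges spread equally over Days 2 to 5; with the 10/20/30/40% spread it is 2.8% to 4.4%. This objection stands.

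**Interval censoring may not cure it.** A reader might infer that the bias would be removed. That holds only if swab timing is non-informative given the covariates. Discharge follows clinical recovery, which may track clearance, and step 5 shows residual bias. This stands, although the residual range is narrower than under the planned rule.

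**The stakes are limited.** No alpha-controlled claim rests on this endpoint, and SAP 5.3.2.2 also models viral load over time by repeated measures. This lowers the priority. It does not correct the medians and ratio that will be reported for this endpoint.

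**Conclusion.** The point holds, at modest size. Two consequences should be kept apart. The overstatement of time to negativity occurs in both arms whichever arm is discharged earlier. It also shrinks any true effect towards 1, even when discharge is equal. The added distortion from unequal discharge is at most about 0.02 on the time ratio when there is no true effect and the planned discharge benefit occurs, and about nil or slightly in pimodivir's favour when discharge is equal or later. The swab schedules and dating rules come straight from the documents. Every bias figure rests on the assumed clearance distribution, the spread of early discharges and the correlation between discharge and clearance, none of which the documents give.

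**What to change.** In SAP 5.3.1.2 and 5.3.2.2, for both qRT-PCR and culture:
- Fit the AFT model (time ratio and medians) with each event interval-censored between the last positive swab and the first confirmed negative swab, using actual sampling times. A negative at the last available assessment still counts as an event, as now.
- Take first dose as the lower bound when no post-baseline positive precedes the event. This matches the SAP's rule that every subject counts as positive at baseline for qRT-PCR; say whether it also applies to culture.
- Right-censor subjects who never become negative at their last positive swab.
- Keep the planned choice of distribution, covariates and bootstrap for the medians.
- State the assumption that swab timing is non-informative given the covariates.
- The stratified Gehan-Wilcoxon test may stay as the main test, with an interval-censored test as sensitivity analysis.

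The cost is SAP wording, a little more programming and slightly less familiar output. No new data, protocol change or alpha adjustment is needed.
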